5.3.5.11 Adverse Events Associated with an Overdose

An overdose is the accidental or intentional use of a drug in an amount higher than the dose being studied. An overdose or incorrect administration of study treatment is not itself an adverse event, but it may result in an adverse event. All adverse events associated with an overdose or incorrect administration of study drug should be recorded on the Adverse Event eCRF. If the associated adverse event fulfills serious criteria, the event should be reported to the Sponsor immediately (i.e., no more than 24 hours after learning of the event; see [Section 5.4.2](#)).

No clinical safety data related to overdosing of MHAA4549A are available, however, overdoses with a monoclonal antibody theoretically could cause volume overload that can result in edema and/or heart failure.

5.4 IMMEDIATE REPORTING REQUIREMENTS FROM INVESTIGATOR TO SPONSOR

Certain events require immediate reporting to allow the Sponsor to take appropriate measures to address potential new risks in a clinical trial. The investigator must report such events to the Sponsor immediately; under no circumstances should reporting take place more than 24 hours after the investigator learns of the event. The following is a list of events that the investigator must report to the Sponsor within 24 hours after learning of the event, regardless of relationship to study drug:

- Serious adverse events
- Non-serious adverse events of special interest
- Pregnancies

The investigator must report new significant follow-up information for these events to the Sponsor immediately (i.e., no more than 24 hours after becoming aware of the information). New significant information includes the following:

- New signs or symptoms or a change in the diagnosis
- Significant new diagnostic test results
- Change in causality based on new information
- Change in the event's outcome, including recovery
- Additional narrative information on the clinical course of the event

Investigators must also comply with local requirements for reporting serious adverse events to the local health authority and IRB/IEC.

5.4.2.1 Events That Occur prior to Study Drug Initiation

After informed consent has been obtained but prior to initiation of study drug, only serious adverse events caused by a protocol-mandated intervention should be reported. A paper Serious Adverse Event Reporting Form and fax cover sheet should be completed and faxed to the Sponsor's Safety Risk Management department or its

designee immediately (i.e., no more than 24 hours after learning of the event), using the fax numbers provided below per region:

Asia Pacific: [REDACTED]

Europe: [REDACTED]

Latin America: [REDACTED]

North America: [REDACTED]

5.4.2.2 Events That Occur after Study Drug Initiation

After initiation of study drug, serious adverse events and non-serious adverse events of special interest will be reported until the patient is at Day 60 or Early Discontinuation. Although the investigator is not required to actively monitor patients for adverse events after the patient has been discharged from the study, the Sponsor should be notified if the investigator becomes aware of any death or other serious adverse event that occurs after discharge from the study, if determined to be related to study drug by the investigator. The Sponsor should also be notified if the investigator becomes aware of a congenital anomaly/birth defect in a subsequently conceived offspring of a female patient exposed to study drug (see [Section 5.4.3](#)).

Investigators should record all case details that can be gathered immediately (i.e., within 24 hours after learning of the event) on the Adverse Event eCRF and submit the report via the electronic data capture (EDC) system. A report will be generated and sent to Safety Risk Management by the EDC system.

In the event that the EDC system is unavailable, a paper Serious Adverse Event Reporting Form and fax cover sheet should be completed and faxed to Safety Risk Management or its designee immediately (i.e., no more than 24 hours after learning of the event), using the fax numbers provided to investigators (see fax numbers provided in [Section 5.4.2.1](#)). Once the EDC system is available, all information will need to be entered and submitted via the EDC system.

Instructions for reporting post-study adverse events are provided in [Section 5.6](#).

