1.3.2.4 Patient Monitoring and Supervision

MHAA4549A will be administered to enrolled patients in a hospital environment under close medical supervision by physician investigators. Medical staff will be available for prompt evaluation and treatment of any adverse events. Emergency resuscitation equipment and emergency facilities will be readily available. Patients will undergo screening assessments to confirm eligibility, will be closely monitored during the administration of MHAA4549A, and will be resident for at least 24 hours following the administration of MHAA4549A. Furthermore, safety laboratory tests relating to the blood chemistries, including liver function tests, will be conducted.

An internal monitoring committee (IMC) in combination with a scientific oversight committee (SOC) will provide safety monitoring for the study in addition to the ongoing review of safety by the Medical Monitor and Safety Scientist. See Section 3.1.2 for more information.

The 120-day follow-up period in the Phase 1 and 2a studies allowed for monitoring of subjects for approximately 5 half-lives of MHAA4549A. No ATAs were detected in the Phase 1 study, while one subject in the Phase 2a study tested positive for ATAs at baseline and post-baseline timepoints as described in Section 1.2.2. The Phase 2b study will also include a safety follow-up period of 60 days and an unlimited collection of all SAEs believed related to MHAA4549A.

Based on the above data and design of this study, the Sponsor concludes that the benefit–risk profile of MHAA4549A in the population with severe influenza is favorable.

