5.3.1 Adverse Event Reporting Period

Investigators will seek information on adverse events at each patient contact. All adverse events, whether reported by the patient or noted by study personnel, will be recorded in the patient’s medical record and on the Adverse Event eCRF.

After informed consent has been obtained **but prior to initiation of study drug**, only serious adverse events caused by a protocol-mandated intervention (e.g., invasive procedures such as biopsies, discontinuation of medications) should be reported (see [Section 5.4.2](#) for instructions for reporting serious adverse events).

After initiation of study drug, all adverse events, regardless of relationship to study drug, will be reported until the Day 60 visit or Early Discontinuation visit. After this period, the investigator is not required to actively monitor patients for adverse events; however, the Sponsor should be notified if the investigator becomes aware of any death or other serious adverse event that occurs after discharge, regardless of causality. The Sponsor should also be notified if the investigator becomes aware of a congenital anomaly/birth defect in a subsequently conceived offspring of a female patient exposed to study drug (see [Section 5.6](#)).

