5.5 POSTSTUDY ADVERSE EVENTS

At the time of study completion or study discontinuation, the investigator should instruct each patient to report to the investigator any subsequent adverse events that the patient or their personal physician believes could be related to prior study drug treatment or study procedures.

The investigator is not required to actively monitor patients for adverse events after the end of the adverse event reporting period (defined as 60 days after the dose of study drug). However, the Sponsor should be notified if the investigator becomes aware of any death, other serious adverse event, or non-serious adverse event of special interest occurring after the end of the adverse event reporting period, regardless of causality. The Sponsor should also be notified if the investigator becomes aware of the development of cancer or a congenital anomaly/birth defect in a subsequently conceived offspring of a female patient or a female partner of a male patient exposed to study drug.

The investigator should report these events by completing and faxing a paper Serious Adverse Event Reporting Form and fax cover sheet to Safety Risk Management using the fax numbers provided to investigators (see [Section 5.4.2.1](#)).

5.6 EXPEDITED REPORTING TO HEALTH AUTHORITIES, INVESTIGATORS, INSTITUTIONAL REVIEW BOARDS, AND ETHICS COMMITTEES

The Sponsor will promptly evaluate all serious adverse events including suspected unexpected serious adverse reactions (SUSARs) and non-serious adverse events of special interest against cumulative product experience to identify and expeditiously communicate possible new safety findings to investigators, IRBs, IECs, and applicable health authorities based on applicable legislation.

To determine reporting requirements for single adverse event cases, the Sponsor will assess the expectedness of these events using the following reference documents:

- MHAA4549A Investigator's Brochure
- Local prescribing information for oseltamivir

The Sponsor will compare the severity of each event and the cumulative event frequency reported for the study with the severity and frequency reported in the applicable reference document.

Reporting requirements will also be based on the investigator's assessment of causality and seriousness, with allowance for upgrading by the Sponsor as needed.

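### Section 5.4.2.2 limits notification of deaths and SAEs after study discharge to related events, 5.3.1 and 5.5 do not, and the sections end the reporting period differently

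*Combined protocol and SAP*

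**What the plan says.** All references are to the combined protocol and SAP, Version 3 (VHP Only), unless another version is named.

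- **Section 5.3.1.** Adverse events "will be reported until the Day 60 visit or Early Discontinuation visit". After that, the investigator need not look for events but should notify the sponsor on learning of "any death or other serious adverse event that occurs after discharge, regardless of causality".
- **Section 5.4.2.2.** SAEs and adverse events of special interest (AESIs) "will be reported until the patient is at Day 60 or Early Discontinuation". After that, the sponsor is to be told of a death or SAE "that occurs after discharge from the study, if determined to be related to study drug by the investigator". For post-study events the section sends the reader to 5.6.
- **Section 5.5.** The reporting period is "defined as 60 days after the dose of study drug", with no mention of early discontinuation. The sponsor is to be told of deaths, SAEs and AESIs "occurring after the end of the adverse event reporting period, regardless of causality". This section also gives the form and route for post-study reports.
- **Section 5.2.1.** Adverse events are monitored to Day 60 or early discontinuation, as in 5.3.1.
- **Section 1.3.2.4.** The study is to include "an unlimited collection of all SAEs believed related to MHAA4549A".

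Section 3.3.3 lists all-cause mortality at Days 14, 30 and 60 as a secondary efficacy outcome.

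**The concern.** A site that learns of a death after a patient has left the study gets a different instruction depending on the section it reads. Under 5.4.2.2, a death that the investigator puts down to influenza need not be notified.

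Two uses of the data could suffer. First, a relatedness filter does not fit an all-cause mortality endpoint. Second, Section 5.6 asks the two monitoring committees (IMC and SOC) to watch influenza disease and its complications for imbalance between arms. Those are the events a blinded investigator is most likely to call unrelated to study drug.

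**Working it through.** **Side by side (Version 3)**

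| Section | Period ends | Deaths and SAEs after that | AESIs after that |
|---|---|---|---|
| 5.2.1 | Day 60 or early discontinuation | not addressed | not addressed |
| 5.3.1 | Day 60 visit or early discontinuation visit | notify, any cause | not listed |
| 5.4.2.2 | Day 60 or early discontinuation | notify only if judged related | not listed |
| 5.5 | 60 days after the dose | notify, any cause | notify, any cause |

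On causality there are two rules: 5.3.1 and 5.5 agree, and 5.4.2.2 conflicts with both. On the end of the period, 5.5 stands alone. On AESIs, only 5.5 extends the duty.

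**Where it came from.** In Version 1, Sections 5.3.1, 5.4.2.2 and 5.5 all applied whatever the cause. The Version 2 summary of changes records the relatedness condition being added to 5.4.2.2. The Version 2 and Version 3 texts of 5.3.1 and 5.5 keep the Version 1 rule. The conflict is therefore inside the protocol text itself, not between a change log and the text. The pointer to 5.6 was already in Version 1; the instructions it means are in 5.5.

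**A worked case.** Suppose a dosed patient leaves on Day 4 without withdrawing consent and dies on Day 12. The investigator learns of the death and judges it due to influenza.

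- 5.3.1: the period ended at the early discontinuation visit; notify anyway.
- 5.4.2.2: the period has ended; no notice is needed, because the death is judged unrelated.
- 5.5: Day 12 is less than 60 days after the dose, so the death falls inside the reporting period.
- 5.3.5.7: deaths attributed solely to influenza go on the Study Completion/Early Discontinuation eCRF, but only within the period set by 5.3.1. That period has closed, so this section assigns the death no form.

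A site can comply with 5.4.2.2 and leave this death unreported.

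**Who is exposed.** For a patient who completes Day 60, the causality conflict concerns only later events, outside the mortality endpoint. For a patient who leaves earlier, it covers the whole interval from exit to Day 60.

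**How much drug is still present.** Section 1.3.2.4 equates 120 days with about 5 half-lives, so the half-life is 120 / 5 = 24 days. The protocol gives no half-life in days against which to check this. Assuming mono-exponential decline, the fraction left t days after the dose is 0.5^(t/24). The range takes 4.5 to 5.5 half-lives in 120 days, that is 120 / 4.5 = 26.7 to 120 / 5.5 = 21.8 days.

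- t = 14: 0.5^(14/24) = 66.7% (64.1% to 69.5%)
- t = 24: 0.5^(24/24) = 50.0% (46.7% to 53.6%)
- t = 30: 0.5^(30/24) = 42.0% (38.6% to 45.9%)
- t = 60: 0.5^(60/24) = 17.7% (14.9% to 21.0%)

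More than half remains only for exits before about Day 24 (range 22 to 27).

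**The case against.** The best defence is that the gap is narrow and partly covered.

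- The Version 2 edit was deliberate, and a related-only rule after study exit matches the promise in 1.3.2.4.
- 5.3.1 and 5.5 keep a passive duty to notify.
- 5.5 has patients told to report later events they think related.
- 4.9.1 asks for every effort to obtain information on patients who withdraw.
- 5.5 carries the post-study title and gives the route, so a careful site would find it.
- Nothing names passive SAE notification as the source of the mortality data. Section 6.4 censors patients lost to follow-up when last known event-free.
- The committees' data flow is set in a separate agreement that is not supplied.
- No rewording recovers patients who withdraw consent, since 4.9.1 ends all follow-up of them.

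Most of this stands as a limit on size. It does not remove the conflict. The safeguards in 1.3.2.4 and in the patient instruction cover only events thought related, so they miss the deaths at issue. The pointer in 5.4.2.2 sends the reader past 5.5. A deliberate edit to one section also leaves the other two saying the opposite.

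A reader might infer a body count: 10% dropout gives 0.10 × 334 = 33 early leavers, and mortality of 9% to 32% gives 33 × 0.09 = 3 to 33 × 0.32 = 11 deaths lost. The documents do not support that.

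- The 10% in Section 6.1 bridges enrolled to evaluable patients. Because efficacy analyses need central PCR confirmation, it may include PCR-negative patients who complete Day 60.
- The mortality range in Section 3.2.2 describes a hospital database. The trial excludes patients with a high probability of death within 48 hours, those on ECMO and those with significant immune suppression, and caps PPV at 45%.
- The product counts all deaths. Those at risk of being lost must follow exit, become known to the investigator and be judged unrelated.

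**Conclusion.** The inconsistency is real in the Version 3 text and should be corrected. Its consequence is limited: a known death or SAE judged unrelated, in a patient who left before Day 60, may go unreported at a site that follows 5.4.2.2. Such a death could then be missing from safety review and, if no other source captures it, from the mortality analysis. The number of events cannot be estimated, because the documents give neither the early-exit rate nor the share of later events known and judged unrelated.

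Three stronger readings are tempting and do not hold. There are not three causality rules, only two. Collection does not stop altogether at early discontinuation; active collection does. Nor is most of the antibody generally still present when reporting narrows. That is so only for exits before about Day 24, assuming mono-exponential decline with a half-life of about 24 days and that experience in healthy volunteers carries over to these patients. At Day 60 about 18% remains.

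Version 5 (Global) is named, but its body is not supplied, so whether it resolves the conflict cannot be checked.

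**What to change.** 1. Put one causality rule and one end of period in 5.2.1, 5.3.1, 5.4.2.2 and 5.5. The sponsor must choose. The rule already in 5.5 (any cause, 60 days after the dose) fits the all-cause mortality endpoint and needs the least new text.
2. State in the same sections whether post-study AESIs are covered.
3. Align 5.3.5.7, whose recording rule depends on the 5.3.1 period, so that a death after early exit has an assigned form.
4. In 5.4.2.2, change the pointer for post-study events from 5.6 to 5.5.
5. Seek vital status at Day 60 for early leavers who have not withdrawn consent.
6. Check first whether Version 5 already does this.

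The cost is amendment wording, one contact per early leaver, and a few more reports to process.

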5.4.3 Reporting Requirements for Pregnancies

5.4.3.1 Pregnancies in Female Patients

Female patients of childbearing potential will be instructed to immediately inform the investigator if they become pregnant during the study or within 120 days after the last dose of study drug. A Pregnancy Report eCRF should be completed by the investigator immediately (i.e., no more than 24 hours after learning of the pregnancy) and submitted via the EDC system. A pregnancy report will automatically be generated and sent to Safety Risk Management. Pregnancy should not be recorded on the Adverse Event eCRF. The investigator should counsel the patient, discussing the risks of the pregnancy and the possible effects on the fetus. Monitoring of the patient should

continue until conclusion of the pregnancy. Any serious adverse events associated with the pregnancy (e.g., an event in the fetus, an event in the mother during or after the pregnancy, or a congenital anomaly/birth defect in the child) should be reported on the Adverse Event eCRF.

In the event that the EDC system is unavailable, a paper Clinical Trial Pregnancy Reporting Form and fax cover sheet should be completed and faxed to Safety Risk Management or its designee immediately (i.e., no more than 24 hours after learning of the pregnancy), using the fax numbers provided to investigators (see fax numbers provided in [Section 5.4.2.1](#)). Once the EDC system is available, all information will need to be entered and submitted via the EDC system.

5.4.3.2 Pregnancies in Female Partners of Male Patients

Male patients will be instructed through the Informed Consent Form to immediately inform the investigator if their partner becomes pregnant within 30 days after the dose of study drug. A Pregnancy Report eCRF should be completed by the investigator immediately (i.e., no more than 24 hours after learning of the pregnancy) and submitted via the EDC system. Attempts should be made to collect and report details of the course and outcome of any pregnancy in the partner of a male patient exposed to study drug. The pregnant partner will need to sign an Authorization for Use and Disclosure of Pregnancy Health Information to allow for follow-up on her pregnancy. Once the authorization has been signed, the investigator will update the Pregnancy Report eCRF with additional information on the course and outcome of the pregnancy. An investigator who is contacted by the male patient or his pregnant partner may provide information on the risks of the pregnancy and the possible effects on the fetus, to support an informed decision in cooperation with the treating physician and/or obstetrician.

In the event that the EDC system is unavailable, follow reporting instructions provided in [Section 5.4.3.1](#).

5.4.3.3 Congenital Anomalies/Birth Defects and Abortions

Any congenital anomaly/birth defect in a child born to a female patient or female partner of a male patient exposed to study drug should be classified as a serious adverse event, recorded on the Adverse Event eCRF, and reported to the Sponsor immediately (i.e., no more than 24 hours after learning of the event; see [Section 5.4.2](#)). Any abortion should be reported in the same fashion (as the Sponsor considers abortions to be medically significant).

5.4.4 Investigator Follow-Up

The investigator should follow each adverse event until the event has resolved to baseline grade or better, the event is assessed as stable by the investigator, the patient is lost to follow-up, or the patient withdraws consent. Every effort should be made to follow all serious adverse events considered to be related to study drug or trial-related procedures until a final outcome can be reported.

During the study period, resolution of adverse events (with dates) should be documented on the Adverse Event eCRF and in the patient's medical record to facilitate source data verification. If, after follow-up, return to baseline status or stabilization cannot be established, an explanation should be recorded on the Adverse Event eCRF and the Investigator document a discharge plan.

All pregnancies reported during the study should be followed until pregnancy outcome. If the EDC system is not available at the time of pregnancy outcome, follow reporting instructions provided in [Section 5.4.3.1](#).

5.4.5 Sponsor Follow-Up

For serious adverse events, non-serious adverse events of special interest, and pregnancies, the Sponsor or a designee may follow up by telephone, fax, electronic mail, and/or a monitoring visit to obtain additional case details and outcome information (e.g., from hospital discharge summaries, consultant reports, autopsy reports) in order to perform an independent medical assessment of the reported case.

5.5 POSTSTUDY ADVERSE EVENTS

At the time of study completion or study discontinuation, the investigator should instruct each patient to report to the investigator any subsequent adverse events that the patient or their personal physician believes could be related to prior study drug treatment or study procedures.

The investigator is not required to actively monitor patients for adverse events after the end of the adverse event reporting period (defined as 60 days after the dose of study drug). However, the Sponsor should be notified if the investigator becomes aware of any death, other serious adverse event, or non-serious adverse event of special interest occurring after the end of the adverse event reporting period, regardless of causality. The Sponsor should also be notified if the investigator becomes aware of the development of cancer or a congenital anomaly/birth defect in a subsequently conceived offspring of a female patient or a female partner of a male patient exposed to study drug.

The investigator should report these events by completing and faxing a paper Serious Adverse Event Reporting Form and fax cover sheet to Safety Risk Management using the fax numbers provided to investigators (see [Section 5.4.2.1](#)).

5.6 EXPEDITED REPORTING TO HEALTH AUTHORITIES, INVESTIGATORS, INSTITUTIONAL REVIEW BOARDS, AND ETHICS COMMITTEES

The Sponsor will promptly evaluate all serious adverse events including suspected unexpected serious adverse reactions (SUSARs) and non-serious adverse events of special interest against cumulative product experience to identify and expeditiously communicate possible new safety findings to investigators, IRBs, IECs, and applicable health authorities based on applicable legislation.

To determine reporting requirements for single adverse event cases, the Sponsor will assess the expectedness of these events using the following reference documents:

- MHAA4549A Investigator's Brochure
- Local prescribing information for oseltamivir

The Sponsor will compare the severity of each event and the cumulative event frequency reported for the study with the severity and frequency reported in the applicable reference document.

Reporting requirements will also be based on the investigator's assessment of causality and seriousness, with allowance for upgrading by the Sponsor as needed.

Certain adverse events are anticipated to occur in the study population at some frequency independent of study drug exposure and will be excluded from expedited reporting. These anticipated events include, but are not limited to, the following:

- Asymptomatic elevations of ALT, AST, and or amylase without corresponding elevations of bilirubin have been shown to be increased during influenza A infection ([Polakos 2006](#))
- Influenza associated disease and or complications of influenza

An IMC and SOC will monitor the incidence of the above-listed anticipated events during the study. An aggregate report of any clinically relevant imbalances that do not favor the test product will be submitted to health authorities.

